The University of Minnesota Child and Adolescent Anxiety Clinic and associated clinics will serve as the primary recruitment site for this study. The Site Principal Investigator, listed below, will oversee participant recruitment and enrollment for this clinical trial.

Principal Investigator

[name], MD
University of Minnesota
Department of Psychiatry & Behavioral Sciences
[name]
[name]
[name]
[contact]
Email: [contact]

Clinical Research Coordinator

University of Minnesota
Study [contact]
Study Email: [contact]

Overview

This is a validation study to evaluate the acceptability, feasibility and impact of WASABI (Wiring Adolescents with Social Anxiety via Behavioral Interventions), a clinician-assisted, adjunct to treatment, mobile application employing a closed-loop technology, designed to augment the efficacy of digitally delivered Cognitive Behavioral Group Therapy (dCBGT). The goal of this study is to evaluate WASABI in adolescents with Social Anxiety and to prepare for a large-scale efficacy trial in this population.

Specific Aims

This study will employ an innovative and evidence-based mobile intervention that includes Ecological Momentary Assessments (EMAs) data collected from mobile devices, the WASABI closed-loop algorithm to detect exacerbation of social anxiety, and 1:1 and group-based videoconferencing and Instant Messaging with peers and providers. This study will test WASABI as an adjunct to dCBGT in adolescents with Social Anxiety (SA), in a parallel arm, double-blind, randomized, controlled clinical trial to assess feasibility and initial efficacy, to investigate the generalization of trained cognitive skills in the natural environment and ability to improve anxiety and social functioning, and to prepare for a large-scale efficacy trial in adolescents with Social Anxiety.

Background

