Participants will be recruited to join a pilot trial prior to the implementation of the parallel arm, double-blind, randomized, controlled clinical trial to assess feasibility and initial efficacy of WASABI as an adjunct to *dCBGT* in adolescents with Social Anxiety (SA). During the pilot trial, three focus groups will be organized with a group of three adolescents with SA and at least one clinician to refine WASABI and qualitatively evaluate its manageability, clinical utility, and acceptability. After the focus groups are completed, participants will be granted access to WASABI for two weeks to test its features and evaluate its usability. At the end of the 2-week trial period, participants will offer feedback on the app through a 1:1 user interview with a member of the research team. It is expected that participants will be enrolled in the pilot trial for approximately 4 weeks.

Participants must be between the age of 14 to 18 (inclusive) and have clinically significant Social Anxiety, as defined by a score of 25 or greater on the Social Phobia and Anxiety Inventory-Brief (SPAI-B) for Adolescents. Participants must have access to reliable Internet connection and must be willing to engage in remote and/or in-person activities to qualify for enrollment.

Prior to initiating any pilot trial procedures, Site Study personnel will screen potential participants (either over the phone or in-person) using an IRB-approved screening questionnaire that assesses for inclusion and exclusion criteria. If the potential participant appears eligible, they and their parents/legal guardian(s), when appropriate, will be invited to a consent/assent discussion with a designated team member prior to enrollment.

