Consenting/assenting to research activities will take place remotely or in a private room at the Study Site. During the consent/assent discussion, the qualified Site Study personnel authorized by the Site Principal Investigator and the potential participant and their parent/legal guardian will discuss the nature, purpose, and procedures of the pilot trial, the possible risks and benefits of participation, confidentiality, and the voluntary nature of participation in the pilot trial (emphasizing the participant's right to withdraw from the focus group at any time). Participants will also be informed of the compensation procedures; specifically, participants will be paid \$10 for completing the consent and screening procedures, \$25 for participating in each focus group session, \$25 for completing 2-weeks of WASABI app activities, and \$15 for completing a 1:1 user interview. Participants that complete all activities will earn a total of \$125. Compensation will be provided through CashPass, a reloadable debit card through a third-party vendor, CT Payer. Payment will be provided upon exiting from the pilot trial, following the completion of the 1:1 user interview. If a participant leaves early, for any reason, and does not complete all focus group activities, they will be paid only for activities they have completed. Upon agreeing to participate in the pilot trial and signing consent/assent documents, participants will be asked to complete the SPAI-B to confirm their eligibility for the study (a score of 25 or greater).

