Once three participants are deemed eligible and enrolled in the pilot trial, they will be scheduled for three focus group sessions that could occur in-person or remotely, to be completed over the course of approximately 2-weeks. Each session will last approximately 1 hour and will be facilitated by the study clinician(s). After feedback from the focus group sessions is implemented into the app and dashboard design, the three adolescents will be granted access to the WASABI app and engage in a 2-week trial period, during which the predictive ability of the algorithm will be validated by the WASABI clinician, who will verify via 1:1 remote videocalls the actual presence of clinically-significant social anxiety whenever the WASABI clinician receives an alert. Additionally, this trial period will ensure that WASABI EMA data are timely evaluated by the clinician on the dashboard and meaningfully orient the delivery of individualized IM and weekly dCBGT content. At the end of the 2-week trial period of WASABI, participants will be asked to rate their enjoyment, ease of use, product quality, and perceived usefulness in a 1:1 user interview. Finally, we will submit these data from the trial period to our consultant to confirm that WASABI is suitable for the feasibility trial.

General Study Design

We will employ a standard prospective, parallel arm, double-blind, randomized, controlled clinical trial to assess the safety and efficacy of WASABI in adolescents with Social Anxiety (SA), and evaluate its potential in augmenting the efficacy of dCBGT in improving social

anxiety, social skills and social functioning. We will randomize adolescents with SA (ages 14-18) to receive either 12 weeks of dCBGT+WASABI or dCBGT only.

Approximately 32 participants will be consented to ensure the successful completion of 24 participants (12 participants per treatment arm). A diagnostic interview will be performed to determine eligibility. Following inclusion and enrollment, participants will complete a set of assessments prior to the intervention to establish their baseline performance. Participants will then be randomized to dCBGT+WASABI or dCBGT only and spend up to 12 weeks engaged in their assigned intervention.

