Experimental Treatment Intervention (dCBGT+WASABI): The Experimental Treatment Intervention is a mobile-delivered and clinically-supervised adjunct to treatment composed of three primary treatment tools. Participants will be asked to 1) attend 12 weekly, 1-hour, group dCBGT sessions and complete "homework" associated with traditional dCBGT; 2) complete 3 EMA sessions per week, weekly standardized SA self-report, and weekly cognitive assessments; 3) use IM for 1:1 and group conversations. At the beginning of each treatment cohort, the WASABI Clinician will create a group text open only to cohort participants, explain their role, and make introductions. Between group sessions, the WASABI Clinician will spend approximately 30 min/day keeping the chat active during work hours, checking it approximately 3 times a day and responding to any messages participants leave, as appropriate. The WASABI Clinician will also receive notifications whenever the WASABI algorithm detects SA symptom exacerbation, and engage participants in synchronous or asynchronous IM. In absence of alerts, the WASABI Clinician will monitor the WASABI dashboard the day before each dCBGT session to customize the delivery of targeted content during the videocall.

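### The pilot's alert-only calls check for the state required at entry, so they can give an alert confirmation rate but cannot show that the algorithm predicts exacerbation

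*Protocol*

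**What the plan says.** The validation is described once, in the protocol under Pilot Trial Design and Procedures. After the focus groups, "the three adolescents will be granted access to the WASABI app and engage in a 2-week trial period", and in that period "the predictive ability of the algorithm will be validated by the WASABI clinician". The clinician does this by 1:1 videocall, verifying "the actual presence of clinically-significant social anxiety whenever the WASABI clinician receives an alert". No call is planned when there is no alert. No reference standard for the call, accuracy target or pass rule is given. The SAP contains no analysis of the algorithm's accuracy.

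The same section sets the entry criterion for the pilot: "clinically significant Social Anxiety, as defined by a score of 25 or greater on the Social Phobia and Anxiety Inventory-Brief (SPAI-B) for Adolescents". The score is confirmed after consent.

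The protocol describes the alert's target in two ways:

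- **Exacerbation.** Specific Aims refers to "the WASABI closed-loop algorithm to detect exacerbation of social anxiety". The end of Background also speaks of patterns of worsening. The Experimental Treatment Intervention text has the clinician notified "whenever the WASABI algorithm detects SA symptom exacerbation".
- **Presence.** The WASABI Alerts item has the alert fire when a participant reaches clinically significant social anxiety, and treats this as the way to address exacerbation. It lists the EMA metrics, the cognitive bias assessments and the SPAI-B as the algorithm's inputs.

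In the pilot the clinician also reviews EMA data on the dashboard. The trial-period data then go to a consultant, who is to confirm that WASABI is suitable for the feasibility trial.

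**The concern.** A claim of predictive ability needs two things: a reference that differs between times when the alert should and should not fire, and observations at both kinds of time. The planned check is weak on the first and lacks the second.

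The reference is presence of a state that all three participants had on entry. Someone who entered well above the cut and has not changed still has it, so an alert on an uneventful day could be confirmed as readily as one on a bad day. The clinician also makes the call because an alert fired, so the judgement is not independent of the alert. A period in which a participant worsened without an alert produces no call and no record in the validation data.

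At stake is what the pilot may claim. Alerts prompt the clinician contact that is part of what separates the experimental arm from dCBGT alone. A high confirmation rate, passed to the consultant as validated prediction, would be read as evidence that the closed loop works, although it could arise from alerts unrelated to symptoms.

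**Working it through.** The documents give no accuracy figure, sample-size argument or pass rule for the validation, so there is no stated figure to reproduce. The check asks what an alert-only confirmation rate can distinguish.

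**Inputs from the documents.** Three adolescents; two weeks; SPAI-B of 25 or greater at entry (3 of 3); calls only after alerts; no calls without alerts.

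**Assumed inputs.** Prevalence *p* of the verified state at call times, 0.80 to 1.00. The entry score shows the state at entry only and does not fix this value. For a useful alert, sensitivity *se* = specificity *sp* = 0.8.

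**Step 1: expected confirmation rate.** This is the positive predictive value:

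PPV = se·p / [se·p + (1 − sp)(1 − p)]

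For an uninformative alert, se = 1 − sp, and the formula reduces to PPV = p.

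| Assumed p | Uninformative alert | Alert with se = sp = 0.8 |
|---|---|---|
| 1.00 | 1.00 | 1.00 |
| 0.95 | 0.95 | 0.76/(0.76 + 0.01) = 0.987 |
| 0.90 | 0.90 | 0.72/(0.72 + 0.02) = 0.973 |
| 0.80 | 0.80 | 0.64/(0.64 + 0.04) = 0.941 |

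The gap is zero at p = 1.00 and about 0.14 at p = 0.80. If the target were exacerbation with an assumed prevalence of 0.2, the same two alerts would give 0.20 and 0.16/(0.16 + 0.16) = 0.50, a gap of 0.30.

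**Step 2: could the pilot see such gaps?** The number of alerts *n* is not stated. I take n = 3, 6 and 18; 18 is 3 EMA sessions per week x 2 weeks x 3 participants, if the trial's weekly minimum also applied in the pilot. As an illustrative rule that is not in the plan, suppose at least 80% of alerts must be confirmed (3 of 3, 5 of 6, 15 of 18). The binomial probability that an uninformative alert meets it is:

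| Assumed p | n = 3 | n = 6 | n = 18 |
|---|---|---|---|
| 0.95 | 0.86 | 0.97 | 0.99 |
| 0.90 | 0.73 | 0.89 | 0.90 |
| 0.80 | 0.51 | 0.66 | 0.50 |

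If every alert is confirmed, the one-sided 95% lower bound for PPV is 0.05^(1/n): 0.37, 0.61 and 0.85 for n = 3, 6 and 18. This ignores clustering within three people. Even 18 of 18 is compatible with an uninformative alert at p = 0.90.

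**Step 3: sensitivity and specificity.** Sensitivity needs the number of true exacerbations without an alert; specificity needs the number of non-exacerbation periods without an alert. Both counts come from alert-free periods, and none of these is verified. Neither quantity can be estimated.

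**The case against.** A reader might go further and infer that the validation cannot fail. The documents do not support that. The protocol does not define the reference used in the videocall, so a clinician could judge the state absent at that moment. A score could also fall below 25 during the roughly four-week pilot. Having 3 of 3 above the cut at entry is a fact about persons at one time, not the prevalence at call times, which is why a range is shown above.

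A reader might also infer that missed exacerbations are invisible. That too goes beyond the text: the clinician reviews EMA data on the dashboard and could notice worsening that raised no alert. But this is informal, and EMA data are themselves algorithm inputs, so it does not provide an independent count of misses.

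The strongest counter-argument is that the WASABI Alerts item words the target much as the pilot words the reference, so the two agree. This shows that the protocol uses presence and exacerbation interchangeably. It does not rescue the check: the trial's inclusion criteria also require an SPAI-B of 25 or greater, so presence has a high base rate at entry under either wording.

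It is also fair that this is a three-person usability pilot with largely qualitative aims, that the consultant receives more than the alert checks, and that no primary or secondary outcome in the SAP uses algorithm accuracy. These points limit the importance of the problem, but the protocol still claims validated prediction.

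**Conclusion.** The point holds in a limited form. The protocol claims that predictive ability will be validated, but the design yields at most an alert confirmation rate against a state with a high base rate. Over an assumed prevalence of 0.80 to 1.00, that rate is 0.80 to 1.00 for an uninformative alert and 0.94 to 1.00 for an alert with assumed sensitivity and specificity of 0.8. Discrimination is therefore weak at the lower end and absent at 1.00, and the few alerts likely in the pilot could not reliably resolve the difference. Sensitivity and specificity are not estimable; that conclusion rests on the sampling of calls and on no assumed number.

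The consequence is confined to what the pilot can say about the algorithm. The trial's outcomes do not depend on it numerically.

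**What to change.** 1. **Reconcile the target.** Make Specific Aims, Background, Pilot Trial Design and Procedures, the Experimental Treatment Intervention text and the WASABI Alerts item agree on what an alert detects. This costs only drafting.
2. **Change the reference.** In each call, have the clinician judge worsening relative to the participant's own entry level, on a short definition written beforehand. The judgement should come from the call, not from SPAI-B or EMA scores, because those feed the algorithm.
3. **Add scheduled calls.** Make a small number at fixed times whether or not an alert fired, by existing staff: for example 2 per week x 2 weeks x 3 participants = 12. The clinician who receives alerts cannot readily be blind to them, so the rating should be recorded before the dashboard is opened where feasible, and any rating made with knowledge of the alert should be marked as such.

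The cost is a few short calls, and the gain is modest. At an assumed exacerbation rate of 20%, 12 calls would include about 12 x 0.2 = 2.4 events. Even if all were detected, the exact two-sided 95% lower bound for sensitivity would be 0.025^(1/2) = 0.16 for 2 of 2, or 0.025^(1/3) = 0.29 for 3 of 3, ignoring clustering. The calls make misses observable; they do not give precise accuracy.

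If calls stay alert-only, replace the claim of validated predictive ability with an alert confirmation rate, and do not present it to the consultant as evidence of predictive accuracy. That costs nothing.

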Participants assigned to receive WASABI will complete at least 3 EMA sessions per week, 1 hour of digitally delivered Cognitive Behavioral Group Therapy (dCBGT) per week, and weekly cognitive biases assessments and self-reports for 12 weeks. During the intervention, these participants will also have daily access to 1:1 and group chat Instant Messaging (IM) and may have weekly electronic check-ins with Site Study personnel (as needed). Participants in the control condition will be asked to attend 1 hour of digitally delivered Cognitive Behavioral Group Therapy (dCBGT) per week for 12 weeks and may have weekly electronic check-ins with Site Study personnel (as needed).

For each arm, as soon as 3-6 participants have completed the baseline assessments and randomization, a cohort will be assembled. The Study Coordinator will meet with the participants to orient them to the study platforms and the WASABI Clinician will meet with each participant individually for a brief introduction and orientation prior to the 12-week intervention and will review of the *Procedures and Guidelines to Group Therapy*. The WASABI Coordinator and/or Clinician will create a virtual support group open only to cohort participants. The WASABI Clinician will explain her role, make group introductions, and will invite participants to attend weekly 1-hour group sessions (dCBGT+ WASABI or dCBGT only, depending on the treatment arm). For the treatment group (dCBGT + WASABI), between group sessions, the WASABI Clinician will spend approximately 30 min/day keeping the chat active during work hours, checking it approximately 3 times a day and may respond to messages participants leave, as appropriate. The WASABI Coordinator will be included in the support group chat and may monitor the chat content, and may be active in the chat in the absence of the WASABI Clinician.

Participants will be re-evaluated again at the expected time of completion, immediately following the 12-week intervention, to evaluate changes in performance. Finally, participants will be asked to fill out an online exit survey to rate enjoyment, usability, perceived benefits, and ease of fit into schedule.

The protocol will be conducted in accordance with the protocol submitted to and approved by the reviewing Institutional Review Board and approval will be obtained prior to implementation.

Study Population

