Digitally delivered Cognitive Behavioral Group Therapy (dCBGT): The WASABI Clinician will lead weekly dCBGT structured sessions through videoconferencing. Sessions replicate the protocol described in "Cognitive-behavioral group therapy for social phobia in adolescents",⁵⁴ with 12 weekly sessions that center CBT content around the young person's developmental context, needs, and capacities, and adapt it to the unique developmental issues characteristic of adolescence (e.g. ascendancy of the peer group, identify formation, propensity towards limit testing). Sessions 1-4 focus on psychoeducation on recognizing and understanding social anxiety symptoms (e.g., avoidance cycle that maintains anxiety over time; rationale for exposure to overcome avoidance cycle). Sessions 5-6 implement cognitive restructuring (focusing on the identification/modification of dysfunctional thoughts) and social skills training. Session 7-8 include instruction in exposure principles and role-play/modeling of exposure exercises. Sessions 9-11 focus on in vivo exposure to anxiety provoking situations. In vivo exposure during these sessions focuses on anxiety provoking situations that can be created within the social setting of the video chat, such as a person giving a speech or singing a song, members engaging in "small talk" with each other, or people altering their appearance in a socially conspicuous way (e.g., messy hair, wearing silly attire). Session 12 focuses on how to avoid personal pitfalls and relapse. Adjustments may be made to the dCBGT treatment

described in “Cognitive-behavioral group therapy for social phobia in adolescents” during COVID-19 to allow for a more appropriate treatment given current shelter-in-place and distance-learning procedures that may not allow for replication of the traditional protocol. Participants are assigned “homework” focused on practicing specific skills in anxiogenic, in vivo situations to promote skills generalization and anxiety/fear extinction learning.

Participants in the active control will complete two sessions of embedded assessments, one immediately before and one after the 12-week intervention. The embedded assessments include two cognitive assessments—an attention bias assessment and interpretation bias assessment—and the SPAI-B assessment.

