The active control program is designed to: 1) be a face-valid approach to remediation in anxiety disorders, to ensure that participants remain blind to group affiliation, and match the experimental treatment program in halo or expectation-based influence on performance in outcome measures; 2) match the experimental treatment program in overall dCBGT session intensity, time-spent attending, and overall engagement; and 3) provide a comparison group that matches the experimental treatment group on the aforementioned attributes, but without the adjunct to treatment component, WASABI.

To use the active control, a participant opens Google Meet, a HIPAA-compliant videoconferencing and instant messaging application on an Internet-connected iOS mobile device and goes to a general log-in screen. The participant then logs in using a study provided account). Participants assigned to the active control are expected to join 12, 1 hour-long dCBGT sessions using the Google Meet application. These will be scheduled and facilitated by the WASABI Clinician. To complete the BrainHQ embedded assessments, a participant opens a standard application (BrainHQ) on an Internet-connected iOS device and goes to a general log-in screen. The participant then logs into the experimental treatment program platform through the BrainHQ application (using a study provided username that contains no personally identifiable information).

Application Security

BrainHQ: All usage and progress data collected through the BrainHQ application is encrypted then transmitted to a central server. Data is encrypted in transit and at rest, and access is limited and audited. Data collected through the BrainHQ platform will not include geographic information. IP address data is stored only in memory and in request logs, and is used for technical support and troubleshooting, but not persisted with the participant's data. However, data as it relates to dates that assessments are completed is collected and stored. The EMA

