G-Suite Google Chat and Meet: This platform allows participants to communicate with others via the app without having to share their full name, mobile phone number or email to do so. Participants also have the opportunity to personalize their profile, by entering a short bio and a picture of their choice. In order to access the Google Meet and Chat apps, participants will have a unique username/login that contains no personally identifiable information. Once logged in, they will be operating within the Google Meet and Chat HIPAA-compliant digital environment, and data that are produced, transmitted, and shared among users will be exclusively visible/readable to the research participants and authorized University of Minnesota and Posit Science staff. These data will include personally identifiable information—such as faces, first names or aliases, biographical and medical information—similar to what happens during all in-person group therapy sessions. The Google Meet and Chat API will allow participants to exchange end-to-end encrypted instant and group messages, as well as make end-to-end encrypted group voice and video calls. Participants will be aware that research team members at the University of Minnesota and Posit Science will have access to the group chat history and will be monitoring its contents throughout the intervention period. As such, participant are informed that any personally identifying information voluntarily shared on this platform will be viewed by staff at both the University of Minnesota and Posit Science. Google Meet and Chat use end-to-end encryption for voice and video calls, as well as instant messages. Google Meet and Chat's voice calls are encrypted with DTLS and SRTP, its video calls with RTP, and its instant messages with RTP. In addition to this, client-server communication is protected by Transport Layer Security. More information about how Google Meet and Chat protects privacy can be found here: <https://support.google.com/a/answer/3407054>

Participants assigned to the Active Control condition will not be asked to use the Google Chat app, as it is unique to the WASABI intervention. Participants in both groups will be able to download other Google apps associated with their deidentified study assigned G-Suite account, such as Google Calendar and Gmail, to facilitate communication with the Site Study team and

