Depending upon the extent to which they are responsible for data collection and/or entry, *Clinical Research Coordinators* may or may not remain un-blinded to participant treatment. This will be clarified on a site-by-site basis and will be noted on the Site Principal Investigator Delegation of Authority Form.

To prevent un-blinding, the following controls will occur at the site level:

1. The treatment condition and the control condition will be identified as “two forms of dCBGT.”
2. Participants will be reminded not to discuss details related to treatment with blinded psychometricians and/or clinical evaluators during the informed consent process as well as prior to initiation, and at the conclusion of, each assessment visit;
3. Site personnel will be instructed to not discuss details of either treatment arm during open participant groups or forums outside of the assigned dCBGT sessions or cohort discussions;
4. Sites will be required execute the protocol in a manner that minimizes the possibility of accidental un-blinding of psychometricians or clinical evaluators (e.g. unintended viewing of treatment sessions).

Research Monitor

This is a minimal risk protocol. There is no significant risk to using either of the web-based programs in this study, beyond the minor discomfort and tedium risks noted above. Previous studies in healthy aging, schizophrenia, and spatial neglect have not noted any significant adverse events arising from program use. Nonetheless, to follow best practices for treatment trials in medical indications, we will employ a central Research Monitor to review all unanticipated problems involving risk to participants, serious adverse effects, and any participant deaths associated with the protocol, and provide an unbiased written report of the event within ten calendar days. The research monitor will comment on the outcomes of the adverse event and relationship of the event to the protocol or test article. The research monitor will also indicate whether they concur with the details of the report provided by the PI.

Reports for events determined by either the PI or Research Monitor to be possibly or definitely related to participation, and reports of events resulting in death will be promptly forwarded to the IRB.

Withdrawal from the Protocol

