7. Reported side effects (raw score). *Based on our previous findings, we expected 0 adverse events due to program use).*

The secondary outcome measures were collected by trained personnel blind to treatment assignment at baseline and after the intervention:

- clinician ratings of anxiety and social anxiety symptoms through the Liebowitz Social Anxiety Scale for Children and Adolescents (LSAS-CA)
- self-report inventories of social anxiety symptoms through the Social Phobia and Anxiety Inventory-Brief (SPAI-B) – at baseline, weekly during the intervention, and after the intervention;
- a broad measure anxiety and potential generalization of treatment to other anxiety domains, the Multidimensional Anxiety Scale for Children 2nd Edition (MASC-2);
- social skills by administering the Social Skills Questionnaire (SSQ) ;
- social functioning using the Adolescent Social Self-Efficacy Scale (ASSES).

The criterion for statistical significance is $p < 0.05$. Results with $p < 0.1$ will be described as trends.

The primary analysis time point is the post-intervention assessment.

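### The trial is called double-blind, but participant blinding is not credible as described, and at least three of the five secondary efficacy measures are self-reported

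*Protocol*

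**What the plan says.** The protocol uses the double-blind label in Specific Aims, in Pilot Trial Design and Procedures, and in General Study Design, which describes a "prospective, parallel arm, double-blind, randomized, controlled clinical trial". Under Active Control Program, the control is said to be designed "to ensure that participants remain blind to group affiliation" and to equal the experimental program in expectation effects. The masking step aimed at participants is in the Blinding section: "The treatment condition and the control condition will be identified as" two forms of dCBGT.

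The activities are described elsewhere. General Study Design states: "Participants assigned to receive WASABI will complete at least 3 EMA sessions per week". It adds weekly bias assessments and self-reports, and daily one-to-one and group messaging. For the control arm, Active Control Program states: "Participants in the active control will complete two sessions of embedded assessments", one before and one after the 12 weeks. Application Security says controls "will not be asked to use the Google Chat app, as it is unique to the WASABI intervention".

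Assessor blinding is set out separately in Study Personnel and Blinding. The clinical rater, all staff who administer and score post-randomization assessments, and the Site PI are blinded. Un-blinded staff may not take part in V3 assessment. Participants are reminded not to discuss their treatment with assessors.

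The SAP (section 2) says the secondary outcomes were "collected by trained personnel blind to treatment assignment". Its list includes SPAI-B measured weekly during the intervention.

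**The concern.** Double-blind normally tells a reader that neither the participant nor the assessor knows the allocation. Here the participant is also the rater for much of the efficacy battery. If participants can tell that they have the app, the chat and extra clinician contact, or that they lack them, then expectation and attention can move their own scores. A blinded member of staff who hands over and scores the questionnaire does not prevent that.

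This bears on what the trial may conclude. Sample Size Justification takes a result below p = 0.05 on the outcome measures as support for saying that the intervention improves social anxiety. The SAP puts weight on a between-arm effect size, and the protocol says the data will be used to power the Phase II trial. A between-arm difference on a self-report scale, presented as double-blind and collected blind, would carry more authority than the design gives it.

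**Working it through.** No sample size, power or alpha figure in the plan depends on this point, so there is no stated figure to reproduce. The check is a count of what each arm visibly does and a classification of who rates each measure.

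**Step 1. What participants experience over 12 weeks** (Protocol: General Study Design, Intervention Embedded Assessments, Experimental Treatment Intervention, Active Control Program, Application Security)

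| Activity | dCBGT+WASABI | dCBGT only |
|---|---|---|
| Group video sessions | 12 | 12 |
| Homework | yes | yes |
| Staff check-ins as needed | possible | possible |
| EMA sessions | at least 3 × 12 = 36 | 0 |
| SPAI-B in the app | 12 weekly, besides the before-and-after sessions | 2 in total |
| Attention and interpretation bias tests | 12 weekly, besides the before-and-after sessions | 2 in total |
| One-to-one and group chat | daily access | none |
| Clinician messages prompted by alerts | yes | none |

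Alerts go to the clinician and are not shown to the participant; the participant sees the message that follows. Active Control Program itself expects that controls may spend less time on study activities. The first three rows match. The other five differ in ways a participant meets every week, and a common name for the two arms does not conceal them.

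**Step 2. Who rates each secondary efficacy measure** (Protocol: Anxiety and Social Anxiety, Data Analysis)

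| Measure | Rater named in the documents |
|---|---|
| LSAS-CA | clinician |
| SPAI (SPAI-B in the SAP list) | participant |
| SSQ | participant |
| ASSES | participant |
| MASC-2 | not stated |

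That gives 3 of 5 stated as self-report, 1 of 5 clinician-rated and 1 of 5 unknown.

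**Step 3. The SAP's blinded-collection sentence against the protocol.** The SAP applies the sentence to the whole list of secondary outcomes, including the weekly SPAI-B. According to the protocol, that scale is completed by the participant inside the BrainHQ app, and weekly in the WASABI arm only. Application Security says the un-blinded WASABI Clinician can review the app data. The description of WASABI Alerts makes SPAI-B one of the inputs that trigger clinician contact. The weekly SPAI-B is therefore not collected by blinded personnel, and it is also part of the intervention. This step needs no assumption about what participants perceive.

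**Step 4. Scope.** The SAP's primary outcomes are feasibility, acceptability and usability measures in the WASABI arm, analysed descriptively. They make no between-arm contrast and do not depend on blinding.

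**The case against.** The strongest reply is that blinding is taken seriously here. The documents specify a blinded rater, blinded scoring, a blinded Site PI, separation of un-blinded staff from V3, and controls against accidental disclosure. The clinician's un-blinded status is openly declared. The control is an active, face-valid treatment, and cohorts are formed separately by arm. The SAP sentence, read literally, describes the collectors and not the participants. The protocol says power is insufficient for an augmentation effect, and the SAP de-emphasizes hypothesis testing.

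Much of this stands, and it rules out several stronger readings:

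- A reader might infer that the trial has no real blinding. The documents do not support that: assessor blinding is specified in detail and covers LSAS-CA.
- A reader might count four of five measures as self-report. That requires assuming a reporter for MASC-2 that the documents do not name.
- A reader might take it as established that participants know their arm. They certainly see their own activities. Whether they know which version is experimental depends partly on the consent text, which is not available.
- A reader might want to attach a size to the reporting bias. The documents give neither an expected add-on effect nor any basis for a bias figure, so none is offered.
- A reader might propose asking assessors to guess the arm. That would test assessor blinding, which is not the weak point.

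The reply does not rescue the participant-blinding claim, because the shared label and the face-valid control leave the visible differences in place. Nor does the literal reading rescue the SAP sentence for the weekly SPAI-B, which staff do not collect. De-emphasizing tests in the SAP does not remove the protocol's statement about p < 0.05.

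**Conclusion.** The point holds in limited form. As described, this is a randomized, assessor-blinded trial whose participant blinding is not credible. At least three of five secondary efficacy measures are rated by participants who experience openly different interventions. The SAP's blinded-collection statement is incorrect for the weekly SPAI-B, and for the other self-report scales it offers no protection against participant expectation. LSAS-CA is the one measure that the documents show to be protected by assessor blinding.

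The conclusion rests on one inference, that such different weekly activities let participants recognise their arm. It is strong but cannot be confirmed without the consent text. The consequence is confined to the secondary efficacy comparison and to what is carried from it into Phase II planning. The direction and size of any bias cannot be determined from the documents.

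**What to change.** 1. Protocol, wherever the design is named: replace double-blind with randomized and assessor-blind.
2. Protocol, Active Control Program: remove the claims that participants remain blind and that expectation is matched between arms. The matching of dCBGT session intensity can stay.
3. SAP section 2: claim blinded assessment only for assessor-rated measures, and state that the weekly SPAI-B is completed in the app and is weekly in the WASABI arm only.
4. Reporting: present SPAI or SPAI-B, SSQ and ASSES as participant-unblinded. State who completes MASC-2 and label it accordingly.
5. Protocol, Sample Size Justification: qualify the sentence on p < 0.05 so that a result on a self-report scale alone is not taken to show that WASABI improves social anxiety. Read LSAS-CA first.

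Parts of the SAP are in the past tense and give a control group of 8, so outcome data may already be in. If so, reading LSAS-CA first should be declared as a later decision made on blinding grounds.

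The cost is wording in both documents and a less favourable design label. No new data collection is needed.
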